## 4 TRIAL OBJECTIVES AND PURPOSE

The present study is designed as a proof-of-concept study to demonstrate clinical activity of RSLV-132 in a cohort of SLE subjects with active cutaneous manifestations of SLE. Evidence of clinical activity is sought in a smaller, more homogeneous subset of lupus subjects prior to embarking on a larger phase 2 dose ranging study.

### 4.1 Primary Objective

- assess the impact of 13 IV infusions of RSLV-132 on cutaneous lupus disease activity using the CLASI activity score comparing Baseline with Day 85 and Day 169 among the drug-treated and placebo groups.

### 4.2 Secondary Objectives

At Days 85 and 169:

- assess disease activity using SLEDAI-2K, BILAG-2004 and PGA;
- evaluate the immunogenicity of RSLV-132 in subjects with SLE;
- assess improvement in tender or swollen joint count;
- assess improvement in patient reported outcomes using the FACIT-Fatigue scale;
- assess the proportion of subjects achieving a 50% improvement in CLASI activity score

At Day 169:

- assess the ability of subjects to reduce oral steroids at Day 169 relative to Day 85;
- evaluate the safety and tolerability of 22 weeks of RSLV-132 exposure;

### 4.3 Exploratory Measures

- evaluate the impact of RSLV-132 treatment on gene expression profile;
- evaluate the impact of RSLV-132 treatment on autoantibody and complement profiles;
- evaluate the impact of RSLV-132 on serum protein levels;
- assess the impact of RSLV-132 on the CLASI damage score

## **5 INVESTIGATIONAL PLAN**

### **5.1 Overall Study Design and Plan**

This is a multi-center, double-blind, placebo-controlled study of approximately fifty subjects with SLE. Potential subjects will be screened to assess their eligibility to enter the study within twenty-eight days prior to study entry (i.e., prior to Baseline visit).

Subjects will be evaluated during screening for evidence of active, evaluable cutaneous manifestations of SLE which will be measured by the investigator using the CLASI score and documented using photography. The photographs will be adjudicated by a dermatologist with expertise in the use of the CLASI tool in SLE clinical trials in order to confirm the subject meets the CLASI entry criteria.

Following Baseline evaluations on Day 1, subjects will receive their first intravenous infusion of RSLV-132. Subjects will return to the research unit for additional visits as described in Appendix A.

The subjects will be randomized 2:1 (active:placebo) to receive IV administrations of 10 mg/kg of study drug or placebo as follows on days:

- 1, 8, 15, 29, 43, 57, 71, 85, 99, 113, 127, 141, and 155

### **5.2 Number of Subjects and Centers**

Approximately 50 subjects will be enrolled at approximately 15-20 clinical centers in the United States, Canada and Europe.

### **5.3 Estimated Study Duration**

Each subject will be screened within twenty-eight days of admission to the study center (Baseline visit). The duration of the study from Baseline visit to End of Study visit, excluding the screening period is approximately 30 weeks for each subject.

## 6 SELECTION AND WITHDRAWAL OF SUBJECTS

Subjects who meet all of the inclusion criteria and none of the exclusion criteria will be eligible to be enrolled into the study.

### 6.1 Subject Inclusion Criteria

Subjects who meet the following criteria may be included in the study:

1. diagnosis of SLE by meeting four of the eleven ACR criteria described in the 1997 update of the 1982 SLE criteria (see Appendix D) including cutaneous involvement at Screening;
2. cutaneous manifestations of SLE and a CLASI activity score of  $\geq 10$  at Screening;
3. elevated levels of any one of the following autoantibodies (local or central laboratory):
  - Ro-52/60, La, Sm, SmRNP, U1 RNP A/68;
4. no changes to SLE medications in the 30 days prior to Baseline;
5. able to communicate and able to provide valid, written informed consent;
6. ages 18 to 70 inclusive;
7. minimum weight of 45 kg;
8. Female participants shall be either of non-child-bearing potential (permanently sterilized by tubal occlusion, hysterectomy, or bilateral salpingectomy, or menopausal more than one year since last menstrual cycle and confirmed by ensuring blood FSH levels  $\geq 22$  mIU/mL); OR practicing highly effective contraception (e.g., oral, implantable, transdermal or injectable contraceptives, a non-hormonal intrauterine device [IUD] with spermicide; female condom with spermicide; contraceptive sponge with spermicide; intravaginal system, diaphragm with spermicide; cervical cap with spermicide; a male sexual partner who agrees to use a male condom with spermicide; a sterile sexual partner) for at least 2 months prior to dosing and until 110 days following the End of Study.
9. Male participants must agree to use a male condom with spermicide from the first dose until 90 days after the last dose. Male participants must agree not to donate sperm from the first dose until 90 days after the last dose.

### 6.2 CLASI Score Entry Criteria – Adjudication

Prior to being enrolled in the study, each patient's cutaneous SLE disease activity measure and photographs of the cutaneous areas of disease involvement will be submitted to and reviewed by an adjudicator. The adjudicator is a dermatologist with extensive experience in reviewing cutaneous clinical data from SLE subjects in a clinical trial setting. The adjudicator will review the photographs of the cutaneous disease to confirm the subject meets the entry criteria and is eligible for the study.

### 6.3 Subject Exclusion Criteria

The following will exclude potential subjects from the study:

1. severe, active CNS involvement at Screening;

2. severe renal involvement (urine protein/creatinine ratio of >200 mg/mmol, or an estimated creatinine clearance of <30 mL/min) at Screening;
3. use of cyclophosphamide within 3 months of Baseline;
4. use of background medications within 1 month of Baseline in excess of:
  - a. mycophenolate mofetil > 3 g/day;
  - b. azathioprine > 200 mg/day;
  - c. methotrexate > 25 mg/week;
  - d. hydroxychloroquine > 400 mg/day;
  - e. prednisone (or equivalent) > 15 mg/day;
5. use of an intravenous corticosteroid “pulse” within 2 months of Baseline;
6. use of an intramuscular steroid injection within 1 month of Baseline;
7. use of rituximab within 6 months of Baseline;
8. use of belimumab within 3 months of Baseline;
9. acute infection or history of acute infection within seven days prior to Baseline;
10. positive viral load test for hepatitis B, C or HIV at Screening;
11. receipt of an investigational product within 3 months of Baseline or five half-lives (whichever is longer);
12. positive pregnancy test at Screening or at Baseline;
13. female subjects currently breast feeding at Baseline;
14. inability or unwillingness to comply with study restrictions, return for follow up appointments, or other considerations, in the opinion of the Investigator, which would make the candidate unsuitable for study participation.

#### **6.4 Subject Withdrawal Criteria**

Subjects will be informed that they are free to withdraw from the study at any time and for any reason. The Investigator may remove a subject from investigational treatment if, in the Investigator's opinion, it is not in the best interest of the subject to continue. Notification of discontinuation of investigational treatment will be made immediately to the Sponsor. In case of premature discontinuation of investigational treatment, efforts will be made to perform all End of Treatment (EOT) assessments and an End of Study (EOS) visit outlined in (Appendix A).

If a subject wishes to withdraw from the study, the site staff should confirm whether the subject is agreeable to continue the assessments without the investigational treatment or if they wish no further involvement in the study. In the latter case no further study-related evaluations will be performed and no additional data will be collected.

The date and the reason for discontinuation of investigational treatment or withdrawal from the study will be recorded on the subject's Case Report Form (CRF). Subjects that withdraw after receiving study drug will not be replaced.

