2.3.5. Subject Withdrawal

Subjects will be informed that they are free to withdraw from the study at any time and for any reason. The Investigator may remove a subject from investigational treatment if, in the Investigator's opinion, it is not in the best interest of the subject to continue. Notification of discontinuation of investigational treatment will be made immediately to the Sponsor. In case of premature discontinuation of investigational treatment, efforts will be made to perform all End of Treatment (EOT) assessments and an End of Study (EOS) visit outlined in SAP Section 2.3.3 Table 1.

If a subject wishes to withdraw from the study, the site staff should confirm whether the subject is agreeable to continue the assessments without the investigational treatment or if they wish no further involvement in the study. In the latter case no further study-related evaluations will be performed and no additional data will be collected.

The date and the reason for discontinuation of investigational treatment or withdrawal from the study will be recorded on the subject's Case Report Form (CRF). Subjects that withdraw after receiving study drug will not be replaced.

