3.2.5. Missing Data and Outliers

Every attempt will be made to capture all study data. For subjects whose visit value is missing, the last observation will be carried forward (LOCF) for the efficacy analyses. Any missing, unused, or spurious data will be noted in the final CSR.

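### Protocol 6.4 does not secure the Day 85 and Day 169 CLASI for subjects who stop treatment early: only EOT and EOS are named, and EOT timing is not given

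*Protocol*

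**What the plan says.** Protocol 6.4 contains two follow-up rules, and SAP 2.3.5 repeats both.

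- **Treatment stops early.** For any early stop, the rule is that "efforts will be made to perform all End of Treatment (EOT) assessments and an End of Study (EOS) visit". It gives no day for the EOT assessments. The SAP version differs only in pointing to its own schedule table.
- **Subject wants to leave the study.** Only here are site staff told to "confirm whether the subject is agreeable to continue the assessments without the investigational treatment".

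EOT is the Day 169 visit in Protocol 12.5 and Appendix A, and it includes CLASI. EOS is Day 215, and neither Protocol 12.6 nor Appendix A lists a CLASI there. The primary endpoints (SAP 9.1) are the changes in CLASI activity from Baseline to Day 85 and to Day 169. Everyone randomized and dosed stays in the efficacy set (Protocol 11.1; the FAS of SAP 3.1.2). For a missing visit value, SAP 3.2.5 states that "the last observation will be carried forward (LOCF) for the efficacy analyses". SAP 9.1 adds an MMRM on observed values.

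**The concern.** A subject who stops infusions but is content to stay in the study is assigned two visits. A subject who asks to leave may be offered all the remaining ones. For keeping outcome data, that is the wrong way round.

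The primary comparison is made at two fixed days in all dosed subjects. A decision to stop treatment is plausibly related to how the skin disease is going, so missing outcomes after a stop are unlikely to be a random subset. Once those days have passed, no analysis method can recover the values: LOCF puts an earlier score in their place, and the MMRM relies on an assumption about the unseen values. With about 33 and 17 subjects per arm, a few such cases carry weight.

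**Working it through.** The plan states no dropout rate, effect size, SD or power, so there is no figure of its own to reproduce. The check sets the follow-up rules against the visit schedule.

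**Inputs.** Infusions are on Days 1, 8, 15, 29, 43, 57, 71, 85, 99, 113, 127, 141 and 155 (Protocol 5.1). Post-baseline CLASI is on Days 29, 57, 85, 99, 113, 127, 141, 155 and 169 (Protocol 12.4, 12.5, Appendix A), before the infusion on dosing days. About 50 subjects are randomized 2:1.

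**Step 1: the two possible timings of EOT.**

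| Stop occurs | EOT at time of stopping | EOT held until Day 169 |
|---|---|---|
| Before the Day 85 visit | Day 85 and Day 169 CLASI not collected | Day 169 collected; Day 85 not explicitly kept |
| Day 85 infusion or later | Day 85 already in hand (pre-dose); Day 169 not collected | Both in hand |

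Only one of the four cells secures both primary days.

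**Step 2: CLASI assessments at stake.** Count the CLASI days later than the last infusion:

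- last infusion Day 1, 8 or 15: 9
- Day 29 or 43: 8
- Day 57 or 71: 7
- Day 85: 6; Day 99: 5; Day 113: 4; Day 127: 3; Day 141: 2; Day 155: 1

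The named follow-up gives 1 in every case, at EOT. After a last infusion on Day 71, that is 7 − 1 = 6 fewer. FACIT is scheduled only at Baseline, Day 85 and Day 169, so an early stop can leave a single post-baseline value.

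**Step 3: what fills the gap.** Suppose the last infusion is on Day 29 and EOT is done on Day 43 (an assumption, since the timing is not given). LOCF carries that score 85 − 43 = 42 days to Day 85 and 169 − 43 = 126 days to Day 169. The MMRM has no observed value on either day. SAP 3.2.8 uses nominal visits without a rule for an early EOT, so the record could also be filed as Day 169.

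**Step 4: how many subjects.** Assuming that 5% to 30% stop early, 50 × 0.05 = 2.5 to 50 × 0.30 = 15 subjects stop. At 2:1 this is about 1.7 to 10 on RSLV-132 and 0.8 to 5 on placebo. Subjects who stop on or after Day 85 already have that value, so fewer are at risk there.

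**Step 5: direction.** Let d be the amount by which a carried score looks better than the unseen one, and let kA and kP be the affected subjects per arm. The apparent benefit of RSLV-132 shifts by kA·d/33 − kP·d/17. With d = 5 points, purely for illustration:

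- one RSLV-132 subject: 5/33 = +0.15
- one placebo subject: −5/17 = −0.29
- three and two: 15/33 − 10/17 = 0.4545 − 0.5882 = −0.13

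If the EOT score is taken during a worsening that later settles, d is negative and every sign reverses. The documents fix neither d nor the split between arms.

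**The case against.** A reader might infer that follow-up depends on who decided, so that subjects taken off treatment by the investigator have no scheduled Day 85 or Day 169 CLASI. The inference is tempting, because the only treatment-stop decision that 6.4 names is the investigator's ("The Investigator may remove a subject from investigational treatment") and the offer to continue is tied to the subject's wish to leave. The text does not support it. The EOT/EOS rule covers any early stop of treatment, including a subject's own choice to end infusions. The written split is between stopping treatment and leaving the study. EOT is itself the Day 169 visit and includes CLASI. Anyone infused on Day 85 or later already has that day's value.

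It can also be said that these subjects leave treatment, not the study, that nothing cancels their visits, and that Protocol 12.1 ties all scheduled visits to days after Baseline. That stands as far as it goes: the Day 85 problem is silence, not exclusion. But 12.1 deals with visit timing and does not mention subjects off treatment. Protocol Appendix E presents the EOT/EOS sentence as the version 5.0 clarification of which assessments early discontinuers should have. A site would reasonably take it as the whole requirement.

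Finally, the study is proof-of-concept, without power calculation or formal testing, and the SAP supplements LOCF with the MMRM and with summaries that censor values after steroid increases or added lupus drugs. This limits the consequence. It does not supply the missing observations.

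**Conclusion.** The point holds as a gap in the follow-up rule. Protocol 6.4 and SAP 2.3.5 name only EOT and EOS after early treatment discontinuation, leave the EOT timing open, and raise continued assessment only with subjects who want to leave the study. Day 169 is lost if EOT is done at the stop. Day 85 is at risk only for stops before Day 85: lost under the same timing, and not explicitly kept if EOT waits until Day 169.

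A reader might go further and conclude that LOCF would inflate the RSLV-132 result by some fraction of a point. The documents do not support that. They give no dropout rate and no basis for the gap between carried and true scores, and affected placebo subjects could offset or reverse the shift. What can be stated firmly is the loss of information: one CLASI in place of up to nine, for subjects who stay in the analysis. The change is worth making but is not critical to the trial.

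**What to change.** In Protocol 6.4 and SAP 2.3.5:

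1. State that every subject who stops infusions, for any reason, is asked to attend the remaining scheduled assessment visits on the original study days without infusion, unless they decline. The minimum is Day 85 and Day 169, with CLASI, the other disease activity scores, joint count, FACIT and steroid dose.
2. Reserve EOT plus EOS for subjects who decline, and state when that EOT is done, so that it is clear which visit its values belong to.
3. Use the Day 85 and Day 169 values collected in this way as observed data in the MMRM and LOCF analyses. Leave the existing censored summaries unchanged.

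The visits and procedures are already in Appendix A, and no dosing, rescue or stopping rule changes. The cost is a short amendment and a few off-treatment visits for a small number of subjects.

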#### **6.5 Women of Child-Bearing Potential**

As women of ages 18 to 70 years old are eligible to enroll in this study, all women will be considered to be of child-bearing potential unless:

- the subject has undergone a surgical sterilization procedure (e.g. bilateral oophorectomy, hysterectomy, or tubal ligation);
- the subject is greater than 12 months past her last menstrual cycle and menopause is confirmed by ensuring blood FSH levels  $\geq 22$  mIU/mL

Pregnancy tests will be performed at Screening, Baseline, and End of Study visits for women of childbearing potential.

## 7 TREATMENT OF SUBJECTS

### 7.1 Description of Study Drug

RSLV-132 is a novel therapeutic candidate. This fully human biologic consists of RNase1 (also known as pancreatic RNase) fused to the N-terminus of the Fc portion of IgG1. The attachment of the Fc domain is intended to extend the serum half-life of the RNase and reduce the frequency of administration. RSLV-132 is provided in single-use vials for dilution for intravenous infusion. Two lots of drug have been used in the study; lot 1-FIN-1778 which was provided at 9.5 mg/mL, and lot 1-FIN-2899 which was provided at 10.0 mg/mL.

### 7.2 Treatment Compliance

Study drug will be administered at the clinical site by trained study staff according to the Study Drug Reference Manual provided by the Sponsor.

### 7.3 Concomitant Medications

Subjects entering the study who had no changes to their SLE medications in the previous 30 days prior to the Baseline visit shall remain on the background medications at the same doses throughout the study. With the exception of decreases in OCS, no changes in lupus medications shall be permitted during the study, including the addition of topical steroids or topical tacrolimus, except for the rescue of a lupus flare.

### 7.4 Steroid Tapering

One of the objectives of the study is to evaluate the potential steroid sparing effects of RSLV-132. Steroid doses should remain stable through Day 85. Thereafter, Investigators shall decrease the use of oral corticosteroids beginning on Day 85 using the guidance below. No further steroid decreases should occur from Day 141 through Day 169.

- Subjects receiving  $>7.5$  mg of prednisone or equivalent daily AND demonstrating a clinical improvement in the cutaneous manifestations of lupus as measured by a decrease in the CLASI activity by 50% compared with Baseline shall decrease oral corticosteroids as follows:
  - Decrease prednisone (or equivalent) by 2.5 mg/day
  - If the prednisone dose (or equivalent) remains greater than 7.5 mg/day AND cutaneous disease activity remains improved (CLASI activity score decreased by 50% compared with baseline) AND prednisone has been stable for 2 weeks, reduce prednisone by an additional 2.5 mg; repeat after 2 more weeks.
  - If prednisone reduced to 7.5 mg, see below,
  - If after a decrease in prednisone, the CLASI is no longer decreased (compared to baseline) by 50%, the investigator may increase the prednisone to the previous daily dose (not to exceed the baseline dose)
- Subjects receiving  $\leq 7.5$  mg/of prednisone or equivalent daily AND demonstrating clinical improvement in the cutaneous manifestations of lupus as measured by a decrease

in the CLASI activity score by 50% compared with baseline, the investigator may, at his/her discretion, decrease prednisone by no greater than 2.5 mg/day every other week.

### **7.5 Treatment of Flares**

Investigators should treat lupus flares as they deem appropriate with the minimum amount of corticosteroid necessary and should return the subject to baseline steroid dose as quickly as medically reasonable. Should a subject require more than steroids for a lupus flare, investigators should treat as necessary and notify the medical monitor.

### **7.6 Randomization and Blinding**

This will be a double-blind, placebo-controlled study. As such, except for the specifically designated unblinded study site pharmacist, the investigator, sponsor, and remaining study site clinical staff will be blinded as to treatment. Ongoing drug accountability will be monitored by an unblinded monitor.

Except in a medical emergency, the investigator or designee and blinded study site clinical staff will remain blinded during the conduct of the study and until such time that all discrepancies in the clinical database are resolved (i.e., at the time of the database lock). The date/initials and reason for the investigator and/or clinical staff removing the study blind will be documented.

## 8 STUDY DRUG MATERIALS AND MANAGEMENT

### 8.1 Study Drug

RSLV-132 is presented as a single-use, preservative-free vial of sterile solution concentrate for dilution for intravenous infusion at a strength of either 9.5 mg/mL or 10.0 mg/mL. The formulation buffer contains 10 mM sodium citrate pH 6.0, 220 mM trehalose and 50 mM L-arginine. All excipients meet multiple compendia requirements and are not of animal origin.

The Sponsor, or designee, will provide the investigator with adequate quantities of the study drugs (see [Table 2](#)).

**Table 2: Study Drug**

Study Drug	RSLV-132
Forma	Sterile injectable solution for intravenous administration packaged in a single-use vial. RSLV-132 will be diluted in saline for infusion.
Strength	Lot 1-FIN-1778, 9.5 mg/mL
	Lot 1-FIN-2899, 10.0 mg/mL

a Specific ingredients/purity will be identified on the Certificate of Analysis (or equivalent) that is supplied with the study drug. The lot numbers for each concentration of the study drugs will be provided to the clinical site by the supplier/manufacture and will be on vial labels.

### 8.2 Placebo

Placebo will be sterile saline for infusion and will be provided by each site and prepared by the unblinded pharmacist.

### 8.3 Study Drug Packaging, Labeling, Storage, Shipping, and Preparation

The study drug will be provided to the sites in single use vials, clearly labeled with drug name and lot number. Study drug will be stored at <-20°C under secure conditions and protected from light. Prior to administration to the subject, individual dosing solutions will be prepared from a vial as detailed in the Study Drug Reference Manual. Details of study drug packaging, labeling, storage, shipping, and preparation, including preparation of matching placebo doses, will likewise be provided in the Study Drug Reference Manual.

